1. Age, body mass index, testosterone, insulin, glucose, and proinsulin levels will be significant predictors of ovulation and conception regardless of treatment.
2. Improvement in body mass index, testosterone, insulin, glucose, and proinsulin levels will be significant predictors of ovulation and conception regardless of treatment.
3. Treatment with metformin XR in combination with clomiphene citrate is more likely to result in singleton pregnancy compared to treatment with Metformin XR alone or clomiphene citrate alone. Singleton pregnancy is defined as presence of an intrauterine gestational SAC with a fetal pole and observable heart motion.
4. Treatment with metformin XR alone or in combination with clomiphene citrate will less likely lead to a first trimester intrauterine fetal demise than treatment with clomiphene citrate alone.

NICHD Reproductive Medicine Network
PPCOS-Pregnancy in Polycystic Ovary Syndrome Protocol

5. Treatment with metformin XR alone is more likely to result in ovulation (increased ovulation rate) compared to treatment with clomiphene citrate. Treatment with both is most likely to result in ovulation.
6. The shortest time to pregnancy will be with metformin XR/clomiphene citrate, followed by metformin XR, followed by clomiphene citrate.

D. Planned / Supplemental Analyses

A set of supplemental analyses/sensitivity analyses, will be conducted to evaluate the effect of treatments by excluding randomized patients who were later discovered to be not eligible, or by excluding patients who did not adhere to the assigned drug regimen.

[figure not shown]
IV. Study Design

A. Overview

The study will be a multicenter, double blind, randomized trial designed to determine the most effective method of achieving a live birth in infertile PCOS women. Patients will be randomized to one of three treatment strategies: 1) metformin XR alone, 2) clomiphene citrate alone, or 3) combined metformin XR and clomiphene citrate.

A1. Schematic of the study design: (see following page)

NICHD Reproductive Medicine Network
 PPCOS-Pregnancy in Polycystic Ovary Syndrome Protocol

NICHD Reproductive Medicine Network
PPCOS-Pregnancy in Polycystic Ovary Syndrome Protocol

A.2 Study Population

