Medication will be adjusted based on progesterone response and side effects. Medication may therefore be adjusted downwards or eliminated to control side effects. These adjustments can take place independently of the DCC by the P.I at each individual site. For instance, if a patient complains of gastrointestinal symptoms (anorexia, diarrhea, GERD, or abdominal discomfort) and evaluation suggests that medication may be responsible the metformin XR/placebo dose should be backed down by 1 tablet per day every week until symptoms subside. If this necessitates stopping medication completely, the patient will be excluded from further study and discontinued. If symptoms subside, after 1 week an attempt should be made to increase the dose by one tablet every 5 days up to 4 tablets a day. Adjustments will be noted on CRFs.

Responders:

Responders will be identified on the basis of an elevated progesterone level consistent with ovulation (Progesterone ≥ 5 ng/mL). One elevated weekly level ≥ 5 ng/mL is evidence of response (36). The rationale for this is that it may not be possible to determine a midluteal peak level, but that two-week levels may overlap the peak and be elevated but not reach peak levels. Therefore we have chosen a middle level between two other cited levels of ovulation, 3 ng/mL and 10 ng/mL. After two consecutive elevated progesterone levels or at the discretion of the investigator, a urine hCG level will be checked. If initial result is negative, continue weekly urine hCG levels until menses. Treatment with all medications will cease from the point hCG is detected. If

NICHD Reproductive Medicine Network
PPCOS-Pregnancy in Polycystic Ovary Syndrome Protocol

ovulatory based on serum progesterone levels, women will continue their medication through menses at the same dose and in the same regimen. After menses from an ovulatory cycle, the patient will again take clomiphene citrate/placebo days 3-7 of the cycle as well as the daily metformin XR/placebo. Responders will continue at the same dose until pregnancy, or until a total of six cycles or until 30 weeks is reached.

Nonresponders:

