There may be breaks in the protocol for both anticipated and unanticipated reasons. Subjects should be counseled that they should be seeking conception for the full potential 30-week period. If personal or professional commitments will result in more than a four-week break from the protocol, subjects should not be enrolled. A break or breaks, up to four weeks, from clomiphene citrate is allowable to facilitate timing of intercourse if there are other commitments. Metformin XR should be continued during this break. Urinary pregnancy tests can be dispensed to check weekly for pregnancy during these breaks. Longer break(s) should be an indication for dismissing the patient from the protocol as non-compliant.

Study Drug Termination Visit:

Patients who conceive, who complete the study without conception or who withdraw will undergo a study drug termination visit as close to their end of medication as possible. The goal of this visit is to determine that there has been no systemic adverse effects of the medication and to obtain follow up sera to identify predictive factors of success. This visit will consist of completion of a CRF, a brief physical which does not require a breast or pelvic exam, and repeat of the safety labs done at baseline. These safety labs include a CBC with platelets, a renal profile, and liver profile. Additionally,

NICHD Reproductive Medicine Network
PPCOS-Pregnancy in Polycystic Ovary Syndrome Protocol

1 ml of serum from one 7.5cc red top tube will be obtained for assay by the central lab.

Serum will be separated, aliquoted, and frozen at -20 to -80 degrees Centigrade until assay by the central lab. A repeat hirsutism assessment will be performed using the Ferriman Gallwey hirsutism scale. Additionally if the patient is pregnant, signed medical release forms should be obtained from the patient to obtain information about the pregnancy outcome-including forms for the prenatal caregiver and the intended hospital for delivery.

Pregnancy Visits:

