PPCOS-Pregnancy in Polycystic Ovary Syndrome Protocol
between the groups of Metformin alone and clomiphene alone. The level of significance for all tests included in the primary analysis will be 0.05.

Supplemental analyses: A set of secondary (supplemental/sensitivity) analyses of the primary endpoint will be conducted after the primary analysis has been performed using the intent-to-treat approach. All secondary analyses of the primary endpoint will be considered exploratory since the study has not been adequately powered for this set of supplemental analyses. Due to the exploratory nature of these analyses, the level of significance for the secondary analyses will be set at 0.05 (two-tailed) to reduce the Type II error rate.

Initially, a comparison of the internal consistency of live birth rates across sites will be examined using logistic regression analysis. Sites with similar live birth rates may be collapsed. For the regression model, the data will be examined to determine whether there is a site by treatment interaction effect. The recommended significance level is an alpha of 0.10 since the power to detect interactions is low. In the event that there is a significant interaction term, clinical site will be included as a covariate in all subsequent secondary analyses.

Next, logistic regression models will be used to evaluate the predictive value of treatment condition, clinical sites (if needed), prior exposure to either clomiphene citrate or metformin XR, and other explanatory factors on live birth rate. Examples of potential explanatory variables include: age, prior parity, body mass index, waist hip ratio, baseline proinsulin, insulin, and glucose values, and baseline testosterone values. In addition, we will examine to what extent change in baseline values is related to live birth rate.

Supplemental sensitivity analysis will also include an analysis of 'evaluable only' patients only (e.g., excluding randomized patients who were deemed to be ineligible later RMN Protocol
08Jan2004

NICHD Reproductive Medicine Network
PPCOS-Pregnancy in Polycystic Ovary Syndrome Protocol
or excluding patients who did not adhere to medication regimen) according to the
protocol).

B. Safety Measures

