- An ovulation will be defined as an elevated weekly progesterone level separated by at least one week with a nonovulatory progesterone level. A binary variable indication whether the patient ovulated or not will be created for each cycle. Furthermore, cycles to first ovulation will be used as time to event variable.
- Time to pregnancy is defined as the number of cycles required to achieve a viable implantation (detection of fetal heart beat). Weeks from pregnancy to live birth will also be used as a time to event variable for patients who did not have miscarriages.
- Conception. Conception is confirmed by a positive serum hCG value. Cycles to first conception will be used as a time to event variable.

E. Drop outs/Treatment Failures

Dropouts, either by patient choice or physician recommendation due to adverse effects or poor compliance will be analyzed by intention to treat as treatment failures. Subjects who have completed 30 weeks or 6 treatment cycles without a pregnancy will also be considered as treatment failures. Subjects who conceive and are lost to follow up will be considered as a treatment success. It is considered unlikely that the patients will be lost to follow-up after a conception on a treatment regimen.

NICHD Reproductive Medicine Network
PPCOS-Pregnancy in Polycystic Ovary Syndrome Protocol

F. Interim Analysis

Analysis Plan: An interim analysis will be conducted on the primary endpoint when 50% of the study participants have completed treatment. The primary analysis described above will be performed and the O'Brien-Fleming (1979) method will be applied to adjust for at the number of looks at the primary endpoint. The interim analysis should also provide a detailed summary of adverse events reported. The critical value for the primary analysis will be specified in the detailed analysis plan. The results of the interim analysis will be submitted to the Data Safety and Monitoring Committee (DSMC). The interim analysis results will be presented in a blinded fashion to the DSMC, who will then evaluate the findings to determine whether the trial should be continued, modified, or discontinued.

Stopping Rules: The stopping rule for the O'Brien-Fleming method compares the statistic Z_i with $Z^*(N/i)^{.5}$, where Z^* is the critical value for the significance level (.05), N is the total number of analyses ($N = 2$) and i is the analysis number (for the one planned analysis, $i = 1$).

VI. DISCLOSURE OF DATA

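### Termination-visit sera are meant to identify predictors of success, but in women who conceive they are drawn after conception, so they should not serve as change-from-baseline predictors of conception or, across all women, of live birth

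*Protocol*

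**What the plan says.** Protocol IV.F, Study Drug Termination Visit, states who attends: "Patients who conceive, who complete the study without conception or who withdraw will undergo a study drug termination visit", and when: "as close to their end of medication as possible". Besides checking safety, the visit is "to obtain follow up sera to identify predictive factors of success". The same paragraph expects some attendees to be pregnant: "Additionally if the patient is pregnant, signed medical release forms should be obtained from the patient".

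IV.F, Responders, states what ends medication in a woman who conceives: "Treatment with all medications will cease from the point hCG is detected". The secondary-measure definitions in section V add: "Conception is confirmed by a positive serum hCG value".

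Two analyses use change in the markers. Secondary hypothesis 2 (III.C) reads: "Improvement in body mass index, testosterone, insulin, glucose, and proinsulin levels will be significant predictors of ovulation and conception regardless of treatment". The supplemental analyses in V.A say: "we will examine to what extent change in baseline values is related to live birth rate". Neither says which post-baseline sample supplies the change.

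Appendix C has serum from baseline, each monthly visit and the termination visit filled into vials for the core lab. Its assays include total testosterone, insulin, proinsulin and glucose, which are all the blood markers in hypothesis 2. The monthly fasting serum has its own stated purpose, in IV.E.3 (Central laboratory) and IV.F: to follow insulin, androgens and other response variables during therapy.

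**The concern.** A predictor has to be measured before what it predicts. Here conception itself triggers the end of treatment, and so the visit at which this serum is drawn. Both the woman's state at sampling (pregnant or not) and her time on treatment at sampling depend on the outcome.

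If early pregnancy alters testosterone, insulin, glucose or proinsulin, a change computed from these sera would be associated with conception even if the marker had no predictive value beforehand. Covariate adjustment cannot repair this for conception, because having a post-conception sample and having conceived are the same thing. At stake is the reading of the exploratory response-predictor analyses.

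**Working it through.** **Order of events, from the protocol's own rules**

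| | Woman who conceives | Woman who does not conceive |
|---|---|---|
| What ends medication | hCG detected (IV.F, Responders) | 30 weeks or six cycles completed, or withdrawal |
| State at termination serum | after conception | not pregnant |
| Time on treatment at that serum | whenever she conceived | about 30 weeks or six cycles, or time of withdrawal |

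For conception, defined by positive serum hCG, the termination serum always follows the outcome. For live birth it precedes delivery, but follows a necessary step towards it.

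**How many women**

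Inputs: planning live birth rates of 25% (clomiphene), 30% (metformin) and 45% (combination), with 226 women per arm (IV.B.5 and IV.B.6); 25% of conceptions lost (IV.B.1, model assumptions).

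- Conception rate = live birth rate / 0.75: 0.25/0.75 = 33.3%; 0.30/0.75 = 40.0%; 0.45/0.75 = 60.0%.
- Women conceiving = 226 × (0.333 + 0.400 + 0.600) = about 301 of 678, before dropout.
- Live births = 226 × (0.25 + 0.30 + 0.45) = 226.
- Conceived without live birth = 301 − 226 = about 75, out of 678 − 226 = 452 women without a live birth (17%).

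A post-conception sample therefore coincides exactly with conception. It overlaps strongly, but not completely, with live birth.

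**What an assumed shift would do (illustration)**

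The protocol has no figure for the effect of early pregnancy on these markers, so the shift d, in SD units, is an assumption shown as a range. Assume no true association before conception and a two-sided test at 0.05, the level set for secondary analyses.

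- θ = δ / √(1/n₁ + 1/n₂); chance of a significant result = 1 − Φ(1.96 − θ) + Φ(−1.96 − θ).
- Conception: n₁ = 301, n₂ = 377, δ = d.
- Live birth: n₁ = 226, n₂ = 452, δ = d × (1 − 75/452) = 0.833d, because some women without a live birth also carry the shift.
- Example, conception with d = 0.1: √(1/301 + 1/377) = 0.0773; θ = 1.29; result 25.3%.

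| Assumed shift d | Conception | Live birth |
|---|---|---|
| 0 | 5.0% | 5.0% |
| 0.1 SD | 25.3% | 17.6% |
| 0.2 SD | 73.5% | 53.4% |
| 0.3 SD | 97.3% | 86.6% |

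With 15% fewer samples (N = 576), the conception figures for 0.1, 0.2 and 0.3 SD are 22.2%, 66.5% and 94.7%. The table shows sensitivity to a shift. It does not show that a shift of any given size exists.

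**The case against.** The strongest reply is that the protocol never says the termination values enter the hypothesis 2 or V.A models. The monthly sera are collected to study change on therapy, and the choice of sample could be settled in the detailed analysis plan that the interim-analysis section mentions and that was not available here. This stands in part, and it makes the point conditional. It does not remove it: the termination visit is explicitly given the predictor purpose, success is not defined there, and nothing restricts the sample to women before conception. An analyst following the text could properly use it.

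Four stronger readings are tempting, and the documents do not support them.

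- A reader might infer that hypothesis 2 cannot be answered. It can, from the monthly fasting sera.
- A reader might infer that stopping metformin by itself creates the association. Every woman is seen near the end of her medication, and the metformin tablets in the clomiphene arm are placebo. What differs is that conception triggers the stop.
- A reader might infer complete confounding for live birth as well. About 75 of the 452 women without a live birth would also have a post-conception sample.
- A reader might take the bias as known to be large. Its size rests wholly on an assumed shift.

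It is also fair to say that the termination serum has a valid predictive use. Among women who conceived, it precedes both loss and live birth, and pregnancy loss is a stated secondary interest. Finally, the affected analyses are declared exploratory and not powered.

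**Conclusion.** The point holds, conditionally. The protocol assigns a predictor role to a sample that, in every woman who conceives, is taken after conception. If the values are used for change from baseline, the time order is reversed for conception, and the marker is partly a consequence of conception for live birth. About 301 of 678 women would have such a sample, which rests on the planning live birth rates, the 25% loss assumption and no dropout. The direction and size of the bias cannot be stated from the documents.

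Only exploratory analyses of response predictors are affected. The randomized comparison of live birth is untouched, as are the baseline predictors in hypothesis 1. This should be corrected in the wording; it is not a threat to the trial's main result.

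**What to change.** Reword the goal of the termination visit in IV.F, and state in V.A (and for the secondary outcomes in V.C) that change predictors of ovulation, conception and live birth use the monthly fasting sera, in one of two ways:

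- as a time-updated covariate: the last value before each cycle, compared with women still at risk at the same cycle; or
- at a fixed landmark, such as the first monthly visit, among women not yet pregnant.

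Taking each conceiver's last sample before her conception cycle is not enough without matching in time. Conceivers would then contribute early samples and non-conceivers late ones, so time on treatment would still depend on the outcome.

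Do not use termination-visit sera as predictors of conception, or of live birth across all women. Keep them for safety, description and, among women who conceived, analyses of later loss versus live birth.

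No new visit, sample or assay is needed. The cost is that women who conceive before the first monthly visit have no on-treatment value and drop out of the landmark analysis; their number should be reported by arm.

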clomiphene citrate alone, metformin achieved a significantly higher ovulation rate than clomiphene citrate alone (20). These women were only followed for 35 days on metformin, but achieved a 35% ovulation rate in this period (20). Studies which systematically examined menstrual regularity in PCOS women on metformin over a longer period of time have noted substantial improvement. Regular cycles, suggestive of monthly ovulation, have ranged from 69-96%(17;21;22). Few studies have addressed the issue of pregnancy in PCOS women on metformin and these have been observational and limited by a small sample size. (17;23) A more complete discussion of these trials is found in discussion of the power analysis below under IV B. Sample Size.

The preliminary evidence suggests that metformin in PCOS women is well tolerated, results in spontaneous ovulation, and is without known adverse effects during early pregnancy. Recently a new sustained release form of metformin, metformin XR with brand name Glucophage XR, has become available, and while similarly efficacious in the treatment of type II diabetes as metformin, it has a more favorable side effect profile. There are no published reports of the efficacy and tolerability of metformin XR in women with PCOS.

III. Objectives

A. Primary Research Hypotheses

The primary hypothesis is that improving insulin sensitivity and inappropriate gonadotropin secretion in infertile women with polycystic ovary syndrome (PCOS) with metformin and clomiphene citrate is more likely to result in a live birth than treatment with Metformin alone or clomiphene alone.

NICHD Reproductive Medicine Network
PPCOS-Pregnancy in Polycystic Ovary Syndrome Protocol
Primary Outcome Measure

The primary outcome measure is the presence/absence of a live birth during the study period. The primary analysis of live birth rate within the three treatment conditions will employ an intent-to-treat approach. Hence, patients will be analyzed according to the treatment group to which they are assigned, even if they did not receive the intended treatment or received only a portion of it.

B. Safety Hypothesis

The hypothesis is that adverse event rates between regimens will be comparable.

Safety Measures

Safety measures will be the number and category of reported adverse events

C. Secondary Research Hypotheses

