The randomization will be integrated into a central Interactive Voice Response System (IVRS) that will be used by the sites to randomize each patient to a treatment condition. For quality control purposes, a second statistician not affiliated with the study will validate the randomization scheme and its transfer to the IVRS randomization database. The IVRS is maintained by the central randomization service, which will provide daily enrollment updates (without treatment assignment indicated) to the DCC project management team. The DCC statistician will review the randomization data on regular basis to ensure that the scheme is being implemented according to plan. If a patient is randomized but never receives treatment, the patient will be considered enrolled in the study. The randomization slot will not be re-allocated to a new patient due to the intent-to-treat nature of the study.

b. Method for notifying investigator of intervention allocation

Randomization will take place only if the patient has met the eligibility criteria and has completed the baseline evaluation. The site investigators will be provided a 24-hour toll free number that will connect to the centralized IVRS.

D. Intervention

Overview of treatment arms: All patients will receive a kit containing metformin XR/placebo or clomiphene citrate/placebo. The active dose of metformin XR will be

NICHD Reproductive Medicine Network
 PPCOS-Pregnancy in Polycystic Ovary Syndrome Protocol

500 mg/tablet consisting of an extended-release tablet given on a two tablets twice per day dosing regimen. The active dose of clomiphene citrate will be 50 mg/tablet, consisting of a generic form. Both investigators and patients will be blinded to the individual contents of the medication kit. Progesterone levels will be obtained at weekly visits. A treatment cycle will consist of either

- 1) an ovulatory response to medication, as determined by weekly progesterone levels followed by either pregnancy or withdrawal bleed, or
- 2) an anovulatory response consisting of 5 consecutive weeks of non-ovulation as determined by weekly serum progesterone levels.

The maximum duration of the study will be six treatment cycles, or 30 consecutive weeks on study drug. If the 6th treatment cycle begins prior to 30 weeks on study drug, the 6th cycle may be completed.

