An inquiry into concomitant medications will be made at the baseline visit as well as each subsequent visit. Use of an exclusionary agent which affects reproductive function or metabolism, such as an anti-diabetic agent, during the study will be prohibited. These medications include oral contraceptives, GnRH agonists and antagonists, antiandrogens, gonadotropins, anti-obesity drugs, somatostatin, diazoxide, insulin, and calcium channel blockers. However it is possible that the P.I. or other physician will prescribe progestins during the study due to abnormal bleeding/prolonged amenorrhea, which will not qualify as a reason for withdrawal. This list will be examined by the P.I. on a monthly basis to determine a suitable course of action. Potential interactions with study medications should also be checked. For instance multiple medications have been shown to increase peak serum levels of metformin (nifedipine, furosemide, and cationic drugs such as morphine, procainamide, triamterene), although half life of metformin is unaffected.

I. Reporting Adverse Events

All serious adverse events (SAE's) throughout study participation from the start of study drug through one week after the last dose of study medication must be reported. For patients who conceive, all SAEs from the start of study drug through delivery/termination must be reported. SAEs should be reported within 24 hours (or 1 business day) of learning of the event to DCRI Safety Surveillance at:

[contact] (telephone)

[contact] (fax)

DCRI Safety Surveillance will forward reportable events to the NICHD within 1 business day of receipt. The NICHD will report serious, drug-related events to the FDA and all RMN Protocol
08Jan2004

NICHD Reproductive Medicine Network
PPCOS-Pregnancy in Polycystic Ovary Syndrome Protocol
participating investigators according to regulatory guidelines. The NICHD will forward relevant safety information to the DSMB as needed. The P.I. will be responsible for notifying their IRB of SAEs in accordance with local guidelines.

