The completed case report forms (CRF) will follow these guidelines: All data on the CRFs will be entered in ink. No data entry in the original CRF may be deleted or corrected by erasure, use of ink eradication fluid or any other such means. When a data entry is in error, draw a single line through the erroneous entry (the original data must remain discernible) and indicate the correct data in whatever way is appropriate. These changes should be initialed by the P.I. or designated study coordinator. Validity of data

NICHD Reproductive Medicine Network
PPCOS-Pregnancy in Polycystic Ovary Syndrome Protocol
recorded on CRFs during each patient visit will be attested to by one of the investigators
by a dated signature on an appropriate CRF page. All questions should be answered.
Data management will be as per DCC guidelines.

R. Competency to perform procedure/tests in the protocol

The principal investigator will be responsible for ensuring that laboratory and patient tests performed as part of the study are performed by competent personnel. These tests include semen analysis, ultrasonography of the pelvis, sonohysterography and/or hysterosalpingography of the uterus and fallopian tubes. The criteria for determination of competency may vary between sites in the study.

V. DATA ANALYSIS

All statistical tests will test non-directional hypotheses. The level of significance will be set at 0.05 for primary analyses and 0.05 for secondary analysis. An intent-to-treat principle will be employed during the primary analysis of the primary efficacy and safety measures. For the intent-to-treat analyses, randomized women will be included regardless of whether or not the patient received the assigned treatment, the patient was compliant with the treatment plan, and/or the treatment was administered according to randomization assignment.

A. Primary Efficacy Measure

Primary Analysis: A live birth will be defined as delivery of any viable infant. The primary analysis of the primary endpoint will include the following procedures. A chi-square test for equal proportions will be performed to evaluate whether live birth rate in Metformin/clomiphene group is the same as one in the group of either Metformin alone or clomiphene alone that has the higher live birth rate. If the test is not significant, a standard chi-square test will be used to examine differences in proportions in live births

NICHD Reproductive Medicine Network

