Adverse Event Analysis: Adverse events will be categorized and percentage of patients experiencing adverse events and serious adverse events during the treatment period will be detailed. Chi-square tests will be performed to examine differences in the proportion of total and categories of adverse events within each treatment arm. For each DSMB report, a list and summary of the reported adverse events will be presented in a blinded fashion, unless otherwise formally requested.

C. Secondary Efficacy Measures

Although not powered to address the secondary outcome parameters, such analyses may provide important pilot data for powering future studies. Multiple logistic regression models will be used in analyses of secondary efficacy measures to evaluate the predictive value of treatment condition, clinical site (if needed), prior exposure to either clomiphene citrate or metformin XR, body mass index, and other explanatory variables on the secondary binary outcomes (e.g., abortion, ovulation). Generalized estimating equations approach will be used if there are multiple outcomes (eg., multiple ovulations) per patient to account correlation within patient. Examples of potential explanatory variables and covariates are: clinical site, prior exposure to either clomiphene citrate or metformin XR, body mass index, age, among others, total testosterone, insulin, proinsulin, and glucose values. Cox proportional hazards models and a Kaplan-Meier method will be applied to compare time to event (eg., cycles to first ovulation, cycles to first conception, cycles to pregnancy, weeks from viable pregnancy to live birth) between the treatment groups.

NICHD Reproductive Medicine Network
PPCOS-Pregnancy in Polycystic Ovary Syndrome Protocol

Due to the exploratory nature of these analyses, the level of significance for the secondary analyses will be set at 0.05 (two-tailed) to reduce the Type II error rate.

Definition of Secondary Measures

- Two different spontaneous abortion rates will be computed. The first is the number of spontaneous abortions over the number of patients who have conceived (defined by positive serum HCG) and the second is the number of spontaneous abortions over the number of patients who are pregnant (defined by detection of fetal heart beat).

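### Safety is analysed by intent to treat while only treatment-period events are counted, so never-dosed women slightly dilute each arm's adverse event percentage

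*Protocol*

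**What the plan says.** The opening paragraph of Protocol Section V sets one rule for efficacy and safety: "An intent-to-treat principle will be employed during the primary analysis of the primary efficacy and safety measures". It then defines the set: "randomized women will be included regardless of whether or not the patient received the assigned treatment". The same sentence keeps a woman in her randomised arm if treatment was not given as assigned.

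Section IV.C.2.a (Randomization Scheme) foresees non-starters: "If a patient is randomized but never receives treatment, the patient will be considered enrolled in the study". Her slot is not given to another patient.

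Events are counted over a narrower window. Section V.B (Safety Measures) says the "percentage of patients experiencing adverse events and serious adverse events during the treatment period will be detailed", and then: "Chi-square tests will be performed to examine differences in the proportion of total and categories of adverse events within each treatment arm". Section IV.I requires serious adverse events to be reported "from the start of study drug through one week after the last dose of study medication must be reported", extended to delivery or termination for women who conceive.

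The safety hypothesis in Section III.B reads: "The hypothesis is that adverse event rates between regimens will be comparable".

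The Protocol names no safety set of treated women. The evaluable-only analyses in Section V.A concern the primary endpoint.

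**The concern.** Numerator and denominator cover different women. A woman who never took a tablet has no treatment period, so under Section V.B she adds to the denominator and cannot add to the count. Each arm's percentage is then lower than the incidence among women exposed to the drug, which is the figure a clinician would want to quote.

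Intent to treat is usually the cautious choice for a superiority claim on efficacy. For harm it works the other way, because pulling percentages and differences toward zero favours a hypothesis of comparable rates. The comparison matters to the trial's conclusion: Section IV.B.4 makes combination therapy the treatment of choice after a positive primary result only if adverse events do not differ significantly.

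**Working it through.** **Arm size.** Section V.B gives no figure of its own, so I take the planned arm size and check it first. For 45% versus 30%, two-sided alpha 0.025, 80% power and no continuity correction, the two-proportion formula gives 197 per arm, as stated in Section IV.B.5. Then 197 × 1.15 = 226.55, which the Protocol cuts to 226 per arm.

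**Dilution formula.** Let p be the event proportion among dosed women and u the never-dosed share, equal across arms.

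- All-randomised percentage: p(1 - u)
- Absolute difference: (p1 - p2)(1 - u)
- Risk ratio: p1(1 - u) / [p2(1 - u)] = p1/p2, unchanged

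**Power formula.** This is a pairwise two-arm chi-square test at two-sided alpha 0.05, with pbar the mean of p1 and p2 and q = 1 - p throughout:

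power = Φ{ [ |p1 - p2|√n - 1.96√(2·pbar·qbar) ] / √(p1q1 + p2q2) }

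For all randomised women, n = 226 with the diluted rates. For dosed women, n = 226(1 - u) with the undiluted rates.

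**Assumptions.** The Protocol gives neither u nor arm-specific adverse event rates. I assume 30% versus 20% for a common event, 5% versus 2% for a rare one, and u from 1% to 10%.

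**Worked case, u = 10%, 30% versus 20%.**

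- All randomised: 27% versus 18%, n = 226. (0.09 × 15.033 - 1.96 × 0.5906) / 0.5871 = 0.333, so power is 63.0%.
- Dosed only: 30% versus 20%, n = 203.4. (0.10 × 14.262 - 1.96 × 0.6124) / 0.6083 = 0.371, so power is 64.5%.

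**Common event, 30% versus 20% among dosed women**

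| u | All-randomised rates | Difference (points) | Power, dosed | Power, all randomised | Loss (points) |
|---|---|---|---|---|---|
| 1% | 29.7 / 19.8 | 9.9 | 68.65% | 68.50% | 0.15 |
| 3% | 29.1 / 19.4 | 9.7 | 67.8% | 67.3% | about 0.4 |
| 5% | 28.5 / 19.0 | 9.5 | 66.85% | 66.12% | 0.7 |
| 10% | 27.0 / 18.0 | 9.0 | 64.49% | 63.05% | 1.4 |

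An outer limit is that the whole planned 15% dropout never starts. The difference is then 8.5 points and power is 62.0% against 59.9%.

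**Rare event, 5% versus 2% among dosed women**

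| u | Power, dosed | Power, all randomised |
|---|---|---|
| 1% | 40.74% | 40.73% |
| 5% | 39.38% | 39.32% |
| 10% | 37.65% | 37.54% |

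The loss is about 0.1 point or less.

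**The case against.** The strongest reply is that the effect is close to nil. The number never dosed is unknown and may be very small, the risk ratio does not move if u is equal across arms, and serious events are rare enough that power hardly changes. The planned test is an ordinary non-directional chi-square with no equivalence margin, so dilution cannot cause a margin to be met. Section V also speaks of the primary analysis and does not forbid a further table in dosed women, which the detailed analysis plan mentioned in Section V.F could add. All of this stands as to size. It does not change the fact that the Protocol itself fixes the primary safety set.

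Two stronger readings are tempting, and the text does not support them.

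- A reader might infer from Section IV.E.6 that many women will never start, because drug begins only after a progestin course and a bleed or a further wait. That matters only if randomisation precedes the progestin. The Synopsis places randomisation after progestin withdrawal, and Section IV.E.3 puts the withdrawal in the screening period and lets it begin straight after the screening visit. The timeline in Section IV.C.1 shows both in week 1. The order is at best unclear, so it gives no basis for expecting a large u.
- A reader might infer that a never-dosed woman cannot have an event recorded at all. Appendix E is broader: it defines adverse events from study initiation and asks for serious events at any time during the study. Such an event could be recorded. It would still fall outside the treatment-period count in Section V.B.

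**Conclusion.** The point holds and is minor. The Protocol states a safety analysis whose denominator includes women who cannot enter its treatment-period numerator. Percentages and absolute differences shrink by the factor (1 - u), toward the hypothesis of comparable rates. For a 30% versus 20% contrast and u of 1% to 10%, this costs 0.1 to 1.0 point of the 10-point difference and about 0.2 to 1.4 points of power.

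These sizes rest on assumed event rates, an assumed u equal across arms, and a pairwise test at 226 per arm. The documents do not support a claim that a safety conclusion would turn on this. The reason to change it is that the reported incidence should describe women who were exposed, and that doing so costs almost nothing.

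**What to change.** In the opening paragraph of Section V, limit intent to treat to efficacy. In Section V.B, define the primary safety analysis as all women who took at least one dose from either bottle, grouped by randomised arm. Every kit holds two bottles, and patients and investigators are blinded (Section IV.D), so starting treatment should not depend on arm and the comparison stays essentially randomised.

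List any wrong-kit cases and show results by kit received as a supportive table only. That grouping departs from randomisation, and blinding does not protect it. Report the number of never-dosed women and any events they had separately. Reconcile the event windows in Sections IV.I and V.B and Appendix E, so that it is clear which events are collected and which are counted.

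The cost is a few sentences, with no new data, visits or patients. The one downside is that safety denominators will be slightly below the number randomised: for example 226 × 0.95 = 214.7, or about 215 per arm, if 5% never start.
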